11.0 DATA REPORTING/PROTOCOL DEVIATIONS

11.1 Data Reporting

11.1.1 Confidentiality and Storage of Records

Electronic Data Collection will be used for this protocol. The data will be stored in encrypted, password protected, secure computers that meet all HIPAA requirements. When results of this study are reported in medical journals or at meetings, identification of those taking part will not be disclosed. Medical records of subjects will be securely maintained in the strictest confidence, according to current legal requirements. They will be made available for review, as required by the FDA, HHS, or other authorized users such as the NCI, under the guidelines established by the Federal Privacy Act and rules for the protection of human subjects.

11.1.2 Subject Consent Form

At the time of registration, the original signed and dated Informed Consent form, HIPAA research authorization form, and the California Experimental Subject's Bill of Rights (for the medical record) and three copies (for the subject, the research record, and the Coordinating Center) must be available. All Institutional, NCI, Federal, and State of California requirements will be fulfilled.

11.1.3 Data Collection Forms and Submission Schedule

All data will be collected using electronic data collection, stored as indicated in Section 12.1.1, and will be submitted according to the timelines indicated in Table 12.1.3.

Table 11.1.3 Data Submission Schedule

Form	Submission Timeline
Eligibility Checklist	Complete prior to registration
On Study Forms	Within 14 calendar days of registration
Baseline Assessment Forms	Within 14 calendar days of registration
Treatment Forms	Within 10 calendar days of treatment administration
Adverse Event Report Forms	For cycle 1 only, within 7 calendar days of AE assessment/notification; for all other cycles, within 10 calendar days of AE assessment/notification
Response Assessment Forms	Within 10 calendar days of the response assessment
Other Assessment Forms (concomitant medications etc.)	Within 10 calendar days of the assessment
Off Treatment/Off Study Forms	Within 10 calendar days of completing treatment or being taken off study for any reason
Follow up/Survival Forms	Within 14 calendar days of the protocol defined follow up visit date or call

Eligibility Checklist

The Eligibility Checklist must be completed by a protocol nurse or clinical research associate and signed by an authorized investigator prior to registering the subject. See Section 4.3 for the registration procedure.

11.2 Protocol Deviations

11.2.1 Deviation Policy

This protocol will be conducted in accordance with COH's "Clinical Research Protocol Deviation Policy" located at <http://www.coh.org/dsmc/Documents/Institutional%20Deviation%20Policy.pdf>.

Deviations from the written protocol that could increase patient risk or alter protocol integrity require prior IRB approval of a single subject exception (SSE) request. In addition, if contractually obligated, the sponsor must also approve the deviation. IRB pre-approved SSE protocol modifications are considered an amendment to the protocol and not a deviation. The submission of a deviation report is not required.

Brief interruptions and delays may occasionally be required due to travel delays, airport closure, inclement weather, family responsibilities, security alerts, government holidays, etc. This can also extend to complications of disease or unrelated medical illnesses not related to disease progression. The PI has the discretion to deviate from the protocol when necessary so long as such deviation does not threaten patient safety or protocol scientific integrity. Examples include, but are not limited to: a) dose adjustments based on excessive patient weight; b) alteration in treatment schedule due to non-availability of the research participant for treatment; c) laboratory test results which are slightly outside the protocol requirements but at levels that do not affect participant safety. These instances are considered to be deviations from the protocol. A deviation report will be submitted to the DSMC/IRB within five days.

11.2.2 Reporting of Deviations

All deviations will be reported to the COH DSMC within five days. The DSMC will forward to report to the IRB following review.

11.2.3 Resolving Disputes

The COH Investigational Drug Service (IDS) cannot release a research agent that would cause a protocol deviation without approval by the PI. Whenever the protocol is ambiguous on a key point, the IDS should rely on the PI to clarify the issue.

In situations where there is misperception or dispute regarding a protocol deviation among the persons involved in implementing the protocol, it is the responsibility of the PI to resolve the dispute and the PI may consult with the DSMC chair (or designee) to arrive at resolution.

12.0 ENDPOINT EVALUATION CRITERIA/MEASUREMENT OF EFFECT

12.1 Toxicity

The primary endpoint is toxicity. Toxicity will be graded according to the NCI-Common Terminology Criteria for Adverse Events version 4.03. Dose limiting toxicity (DLT) is defined in section 13.2 of the protocol. The MTD will be based on the assessment of DLT during cycle 1.

12.2 Response

The primary endpoint is complete remission rate (CR + CRi) and is based on the Döhner, 2010 criteria²⁴; calculated as the percent of evaluable patients that have confirmed CR or CRi.

Response criteria will be as follows:

CR: Bone marrow with < 5% blasts by morphology. ANC > 10³/µL, platelets ≥ 10⁵/µL

CRi: Bone marrow with < 5% blasts by morphology, not meeting blood count criteria for CR.

PR: Decrease of at 50% in bone marrow blasts

PD: Bone marrow blasts more than 20% and increase in blasts by over 50%.

HR: improvement in hematologic parameters, but not meeting criteria for PR.

Secondary activity endpoints for this study are as follows:

- Duration of response, defined as the time interval from the date of first documented response (CR+CRi) to documented disease relapse or death whichever occurs first.
- Overall survival, defined as the time interval from date of first dose of study drug to date of death from any cause.
- Event-free survival, defined as the time interval from date of first dose of study drug to first documented disease progression or death from any cause, whichever occurs first.
- Overall response rate (CR/CRI/PR), calculated as the percent of evaluable patients that have confirmed CR or CRi or PR.

12.3 Clinical Pharmacology Endpoints:

- For plasma PK, levels of 8-chloro-adenosine, its deaminated metabolite, 8-chloro-inosine, and its base 8-chloro-adenine will be quantitated in plasma during 5 days of therapy.
- For cellular PK, concentrations of 8-chloro-adenosine and 8-chloro-ATP will be quantitated in circulating leukemia cells in the peripheral blood.
- For urine PK, levels of 8-chloro-adenosine, its deaminated metabolite, 8-chloro-inosine, and its base 8-chloro-adenine will be quantitated in urine during the first 24 hours of therapy.
- For PD, the impact of therapy on endogenous ATP pools, as well as the effect on short-lived mRNA transcripts and proteins will be analyzed in circulating acute leukemia blasts.

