1.2 Secondary Objectives

Phase I:

To evaluate for disease response to 8-chloro-adenosine in refractory/relapsed AML on each dose level tested.

Phase II:

To obtain estimates of remission duration and survival probabilities (overall and event-free).

To obtain an estimate of the overall response rate (CR+CRi+PR).

To summarize and evaluate toxicities by type, frequency, severity, attribution, time course and duration.

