5.2 Treatment cycle definition

Participants will be treated in 28-day treatment cycles until disease relapse, progression, unacceptable toxicity, withdrawal of consent, or other protocol specified parameters to stop treatment.

Once a treatment cycle has began (i.e. the Day 1 dose administered) if there is a hold in administering the study agent (see section 6.3.2), **missed doses may be made up if the criteria to resume treatment are met within 48 hours, or by Day 5 of the treatment cycle, whichever is later**. Otherwise missed administrations will not be made up, and treatment will resume with the next cycle (assuming start of cycle criteria are met). Should a hold or delay in treatment occur, after the last dose is administered in a given cycle, there will be a 21 day break, which may result in a delay in the start of the subsequent cycle.

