5.7 Duration of Therapy & Criteria for Removal from Study Treatment

Duration of therapy will depend on individual response, evidence of disease progression and tolerance, or completion of 4 cycles of study treatment. Patients may continue for up to 4 cycles of treatment unless unacceptable toxicity or disease relapse/progression. In the absence of treatment delays due to adverse events, treatment may continue until one of the following criteria applies:

- Participant demonstrates disease progression.
- Intercurrent illness that prevents further administration of treatment
- Unacceptable adverse event(s) (see Section 13.2, 6.3.1)
- Participant withdraws from the treatment phase of the study
- General or specific changes in the participant's condition that render the participant unacceptable for further treatment in the opinion of the treating investigator.

Documentation of the reason for discontinuing therapy and the date effective should be made in the medical record and appropriate eCRF. The participant should then proceed to off-treatment procedures for safety monitoring and follow-up procedures. The participant status is to be modified in the MIDAS system once the off-treatment period is completed. Alternative care options will be discussed with the participant.

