- c. Participants will receive a maximum of 4 study cycles. Participants who experience unacceptable toxicity or disease progression after cycle 2 will forgo additional treatment cycles and proceed to the 30-day-follow-up visit. There will be a +7 day window for start of cycles 2-4.
- d. Day 1 assessments (including EKG) to be performed prior to Day 1 drug. Start of cycle criteria (Section 6.2) must be met before administering Day 1 study agent.

- e. Study agent will be administered daily for five consecutive days. EKG will be performed and reviewed prior to study drug administration. See section 5.2: 'Treatment Cycle Definition' for additional detail regarding treatment administration timing in the event of a hold.
- f. Window for Day 8, 15, and Day 22 assessments is the stated day +/- 2 days. Bone marrow biopsy may be performed between days 22 and 28 after cycle initiation.
- g. Window for the 30-day Post Last Dose visit is +/- 2 days. All participants will be followed until resolution or stabilization of any related serious adverse events occurring during treatment or starting within 30 days of last study drug administration.
- h. Active follow-up will occur for participants who have completed EOT procedures and yet to demonstrate disease progression. The active follow-up visit will take place every 28 days (+/- 5 days) from the day of the EOT Day 30 visit. Active follow-up will continue until an alternative acute leukemia therapy has commenced or until disease progression or up to 2 years following first study agent administration.
- i. Survival follow-up will occur approximately every 3 months (+/- 14 days) from Off-Therapy date for survival status and will occur for up to 2 years following the participant's first study agent administration. Information will be obtained via medical record review, use of the social security registry, or by telephone contact.
- j. Documented informed consent to occur prior to any study related procedures that are not otherwise SOC.
- k. Medical history to include review treatment history for AML, relevant medical history pertaining to study eligibility, and demographic information.
- l. Concurrent medications, supportive care, blood products, or radiation therapy taken or administered during the trial will be documented in the subject's medical record using institutional documentation guidelines. See Section 5.11 for prohibited therapies.

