13.3 Dose Escalation/Expansion

The phase I study will follow a modified 3+3 design. During dose-doubling, enrollment and dose escalation of a cohort will be on the basis of the occurrence of moderate and/or dose limiting toxicities (DLTs). If dose-doubling is ended by a single DLT in cycle 1 or two occurrences of 'moderate' treatment-related

toxicity, subsequent dosing will be based on DLT only. DLT and moderate toxicity incidence will be based on toxicity events encountered during the first cycle of 8-chloro-adenosine treatment.

This modified design involves an initial accelerated dose escalation stage (dose-doubling over 'a' levels) that may be ended by a single dose-limiting toxicity (DLT) in cycle 1 or two occurrences of 'moderate' treatment-related toxicity as defined in section 13.2. During the initial accelerated stage of accrual, cohorts of up to 3 patients will be enrolled and the dose level will be escalated by increments of 100% (skipping 'b' dose levels). If two patients encounter moderate toxicity or one patient encounters DLT during cycle 1, the current dose level will be expanded and the accelerated stage will end; dose-doubling will stop. At the conclusion of the accelerated stage, dose escalation will occur over 'a' and 'b' dose levels according to the following rules*:

- If zero out of 3 evaluable patients has a DLT in cycle 1 then the next dose of 8-chloro-adenosine will be tested.
- If 1 out of 3 evaluable patients has a DLT in cycle 1, three additional patients will be assessed at the same dose of 8-chloro-adenosine.
- If 2 out of 3 patients have a DLT in cycle 1, dose escalation will cease and the next lower dose level will be expanded. Note: If 2 of 3 experience DLT on dose level -1, the trial will be stopped. Dose levels below 50mg/m² will not be considered.
- If 1 out of 6 evaluable patients has a DLT in cycle 1, then dose escalation to the next dose of 8-chloro-adenosine will continue.
- If 2 or more out of 6 patients have a DLT in cycle 1, dose escalation will cease and the next lower dose level will be expanded. Note: If 2 of 6 experience DLT on dose level -1, the trial will be stopped. Dose levels below 50mg/m² will not be considered.

The highest dose level that produces $\leq 1/6$ DLTs in cycle 1 will be the maximum tolerated dose (MTD). Patients may continue therapy unless there is unacceptable toxicity, disease relapse/progression or withdrawal of consent.

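### Section 12.2 does not name relapse as an EFS event, so EFS can outlast the remission; Kaplan-Meier for time to response can exceed the proportion responding (minor)

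*Combined protocol and SAP*

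**What the plan says.** Section 12.2 lists the secondary activity endpoints. Duration of response runs from the first documented CR or CRi "to documented disease relapse or death whichever occurs first". EFS runs from the first dose to "first documented disease progression or death from any cause, whichever occurs first". The progression criterion in the same section is "PD: Bone marrow blasts more than 20% and increase in blasts by over 50" per cent. CR and CRi both need fewer than 5% marrow blasts. The section gives no criterion for relapse, and it does not say whether the 50% increase is counted from the pre-treatment marrow or from the lowest value reached.

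Other sections use the two terms differently. Section 5.2 treats patients "until disease relapse, progression, unacceptable toxicity, withdrawal of consent", with relapse and progression as two items. Sections 5.7 and 13.3 join them: "unless unacceptable toxicity or disease relapse/progression" and "unless there is unacceptable toxicity, disease relapse/progression or withdrawal of consent". Study calendar footnote h (section 10.0) has no separate exit for relapse: "Active follow-up will continue until an alternative acute leukemia therapy has commenced or until disease progression or up to 2 years". Footnote u schedules marrow after cycles 1 and 2 and when needed to confirm a response. It also lets the day 22 marrow be omitted when circulating blasts have risen by 50%.

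Section 13.7 and its synopsis copy apply the product-limit method to time to response as well as to duration of response and survival. Neither gives a population for time to response, a censoring rule, or the handling of death or new therapy before response. The CR+CRi rate is a percentage of evaluable patients. Section 13.1 counts a phase II patient as evaluable after two cycles, or after one if CR or CRi was reached.

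**The concern.** Section 1.2 puts remission duration and EFS under one phase II secondary objective, yet the two definitions can give different dates for the end of the same remission. A responder whose remission has ended can still count as event-free.

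Time to response has a different problem. Kaplan-Meier treats a censored patient as someone who could still respond later. A patient who has died, or whose response assessment has stopped because of new therapy, cannot. Censoring such patients hands their share of the curve to later responders, so the curve can end above the proportion who responded in the population it describes.

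At stake is the reading of two descriptive summaries in at most 25 patients.

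**Working it through.** **The plan's own figures.** None bears directly on EFS or time to response. The stage 1 figure reproduces: 1 - 0.7^9 = 0.960, against the stated 96%. So does the largest standard error: sqrt(0.25/25) = 0.10. Nothing below changes either.

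**1. Which lost remissions meet PD?** Apply the section 12.2 rule (above 20% and an increase above 50%) to a patient who was below 5% blasts.

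- At 5, 10, 15 or 20% blasts, PD is not met with any reference, because the 20% condition fails.
- At 21% against a nadir of 4%, PD is met.
- At 60% against a pre-treatment value of 50%, the increase is 20%, so PD is not met.

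The 5% lower end is inferred from the CR/CRi criteria, because the section has no relapse rule.

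**2. Size for EFS (all rates assumed).** Median remission is 6 months (l1 = ln2/6), median time from relapse to PD or death is 2 months (l2 = ln2/2), CR+CRi is 10-30%, and 25-50% of relapses do not meet PD. That last range takes the nadir reference. For a responder whose relapse is not PD, the chance of being relapsed but still counted event-free at time t after response is

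l1/(l2 - l1) x [exp(-l1 t) - exp(-l2 t)].

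This peaks at t = ln3/(l2 - l1) = 4.8 months, at 0.5 x (0.577 - 0.192) = 0.192.

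- Low: 0.192 x 0.10 x 0.25 = 0.5 points, or 0.12 of 25 patients.
- High: 0.192 x 0.30 x 0.50 = 2.9 points, or 0.72 of 25 patients.
- The area under the formula to 24 months is 2.615 months. Restricted mean EFS is therefore longer by 2.615 x 0.025 = 0.07 to 2.615 x 0.15 = 0.39 months.
- Outer bound, if no relapse met PD and the other rates are kept: 0.192 x 0.10 = 1.9 to 0.192 x 0.30 = 5.8 points.

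For scale, the standard error of a 40% proportion at n = 25 is sqrt(0.4 x 0.6/25) = 9.8 points.

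**3. Time to response (rates assumed).** Take four cycles, with a chance r of response and d of loss before response in each.

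- All treated, proportion responding: sum over k = 1 to 4 of r(1 - r - d)^(k-1).
- All treated, 1-KM: 1 - (1 - r)^4 if losses are censored at the cycle-end assessment, or 1 - [1 - r/(1 - d)]^4 if censored earlier in the cycle.
- Strictly evaluable (non-responders lost in cycles 1-2 removed): the denominator is D = 1 - d - d(1 - r - d). The proportion is the sum above divided by D. 1-KM is 1 - [(1 - r - d)^2/D] x (1 - r)^2, or the same with r/(1 - d) in place of r in the last factor.

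| r, d | Population | Responding | 1-KM |
|---|---|---|---|
| 8%, 25% | strictly evaluable (D = 0.5825) | 33.2% | 34.8-38.5% |
| 8%, 25% | all treated | 19.4% | 28.4-36.3% |
| 5%, 20% | strictly evaluable (D = 0.65) | 21.0% | 21.9-23.9% |
| 5%, 20% | all treated | 13.7% | 18.5-22.8% |
| 8%, 0% | all treated | 28.4% | 28.4% |

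A worked case with 5 responders among 25 (2 after cycle 1, 3 after cycle 2; 20.0%) shows what drives the gap. With 3 non-responders censored in cycle 1 and 5 in cycle 2, 1-KM = 1 - (1 - 2/22)(1 - 3/15) = 27.3%. With no one censored before the last response, 1-KM = 1 - (1 - 2/25)(1 - 3/23) = 20.0%. In responders only, both figures are 100%.

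**The case against.** The strongest reply on EFS is that the protocol means relapse to count as progression. Section 5.7 opens with the paired term and then lists only progression as the disease reason for stopping. Sections 5.1, 5.9 and 5.10 and calendar footnotes c and h also use progression alone. If relapse were something else, relapsed patients would remain in active follow-up, which is hard to square with section 5.7. This is a good argument, and under that reading the EFS gap is zero. But no section says it, section 5.2 lists the terms separately, and section 12.2 uses different words for two endpoints in one list.

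On time to response, the reply is that it is not among the endpoints in section 12.2 or the objectives in section 1.2, and that response is otherwise analysed in evaluable patients. Few evaluable patients can be lost before the end of cycle 2, and scheduled marrows fall after cycles 1 and 2. If all responses come by then without earlier censoring, there is no gap. That stands, and it makes the evaluable rows the more relevant ones. It does not remove the point, because response is assessed at the end of every cycle, up to four, and the population is not stated.

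All the sizes rest on assumed rates. That is true, and it is why only the direction is firm.

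**Conclusion.** The point holds as a minor one. As written, a remission lost at 20% marrow blasts or below is not an EFS event. Above 20% the answer depends on the unstated reference for the increase. The EFS curve is then too high by 0.5-2.9 points at its peak, under one patient in 25, on assumed rates that take the nadir reference. Time to response by Kaplan-Meier exceeds the proportion responding whenever non-responders who die or start new therapy are censored before a later response. At 8% response and 25% loss per cycle this is 35-39% against 33% in strictly evaluable patients.

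Four stronger readings do not follow from the documents:

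- A reader might infer that EFS misses every relapse. It does not: a relapse above 20% blasts meets PD if the increase is taken from nadir. The opposite claim, that every marrow-documented relapse above 20% is captured, fails too, because the reference is not given.
- A reader might take 28-36% against 19% as the expected distortion. Those figures are for all treated patients, a population the plan does not name for response.
- A reader might count the missing rule for new therapy in EFS as a further error. It is missing detail. New therapy is not in the list of EFS events, and only its handling as censored or ignored is left open.
- A reader might carry the point over to the main result. The CR+CRi rate is a simple proportion and the Gehan rule counts responses, so neither is affected.

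**What to change.** **EFS (section 12.2).** Define the event as the earliest of relapse after CR or CRi, progression, or death. State the relapse rule once and use it for duration of response as well. The sponsor should state the reference value for the PD increase and reconcile the marrow-based definition with the schedule and permitted omission in calendar footnote u. No clinical criterion is proposed here.

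**Time to response (section 13.7 and its synopsis copy).** Estimate it by cumulative incidence in the evaluable population used for the CR+CRi rate, with death or new therapy before response as competing events. Say also how a patient whose response assessment ends at progression is handled, because censoring there would bring the gap back. Footnote v lets patients go on to cycle 2 whatever the cycle 1 result, so later responses must still count. A descriptive summary in responders only would also do. Keep Kaplan-Meier for overall survival, EFS and duration of response.

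**Cost.** A few sentences and minor programming. The relapse date is already needed for duration of response, and later anti-cancer treatment and survival are already collected (footnotes cc, dd and ee). EFS and the response curve may look slightly less favourable.
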